6.1 STUDY AGENT(S) AND CONTROL DESCRIPTION

This study will test a nitrate intense vs. diuretic intense early AHF strategy. No investigational therapies will be used. No drugs or therapies that are not approved by the FDA will be allowed.

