10.4 DESCRIPTION OF STATISTICAL METHODS

10.4.1 GENERAL APPROACH

As a small, exploratory, pilot study, we are uncertain the difference, if any, between the two arms in regards to B-lines after treatment. Unless stated otherwise, two-sided p values < 0.05 will be considered statistically significant, without regard to multiple comparisons. Statistical tables and listings and analyses will be produced using SAS® release 9.1 or later (SAS Institute, Inc, Cary, NC, USA) or other validated statistical software.

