10.4.3 ANALYSIS OF THE PRIMARY EFFICACY ENDPOINT(S)

The total number of B-lines at the conclusion of ED AHF management

We will examine the distribution of B-lines measurements for the groups with and without events separately. Both absolute number and relative change will be evaluated. Receiver Operating Characteristic (ROC) curves will be plotted together with area under the curve (AUC) calculated to understand the prediction performance of the B-line measurements. Sensitivity, specificity, positive and negative predictive values will be computed at a number of thresholds of B-line measurements to understand the trade-off between false positive and false negative. Confidence intervals of statistical measures will be constructed using the bootstrap method.⁹¹ Although 15 B-lines have been previously identified as a valid threshold, an alternative number may be more useful in the ED setting.

Potential covariates will also be considered in a logistic regression setting to improve precision, which includes baseline co-morbidities, baseline medications (in particular guideline recommended therapies) in-hospital medications, baseline renal function, serum sodium, natriuretic peptide levels, troponin levels, renal function, baseline blood pressure, and discharge medications. Variables such as physical exam, other vital signs, and hemoconcentration may also be included. These covariates are known markers of risk and are standard of care assessments for the vast majority of AHF admissions. Covariates with univariately significant association with the outcome will be included together with the treatment indicator in a logistic regression model. Due to limited sample size, we will limit the number of covariates (including treatment indicator) such that there is 10 events per covariate.

ANALYSIS OF THE SECONDARY ENDPOINTS

1. Dyspnea will also be assessed using a 5-point and 7-point Likert scale.

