10.5 SAMPLE SIZE OVERALL

This pilot study is powered to show a difference of at least 7 B-lines between treatment arms. With a total of 70 subjects (i.e. 35 in each arm), we will have 82% power to detect an effect size of 0.7 on the number of B-lines, where the type I error rate is controlled at 0.05 (two sided)..

Local Sample Size: As a multicenter study, the expected enrollment at IU is half the patients or 35. However, up to 50 patients may be enrolled depending on accrual rates at the other site.

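### The logistic model in 10.4.3 that carries the treatment indicator can admit covariates measured after randomisation, including in-hospital and discharge medications, which can bias the arm effect

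*Combined protocol and SAP*

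**What the plan says.** All references are to the combined protocol and SAP.

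- **Candidate covariates (10.4.3, primary efficacy endpoint).** After baseline comorbidities and baseline medications, the list continues "in-hospital medications, baseline renal function, serum sodium, natriuretic peptide levels, troponin levels, renal function, baseline blood pressure, and discharge medications". The next sentence adds physical examination, other vital signs and hemoconcentration as possible extras.
- **Entry rule (10.4.3).** "Covariates with univariately significant association with the outcome will be included together with the treatment indicator in a logistic regression model". The number of terms, treatment included, is capped so that there are 10 events for each. The declared purpose of adjustment is precision.
- **Randomised contrast (6.1).** "This study will test a nitrate intense vs. diuretic intense early AHF strategy". Section 6.1.2 lets the protocol run on after the patient reaches the floor.
- **Timing of the primary endpoint (Protocol Summary).** Total B-lines when emergency-department management ends, or at 6 hours after enrolment if that is sooner.
- **Contrast within the plan (10.4.4).** The proportional odds model for days alive and out of hospital refers to baseline covariates only.

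**The concern.** Covariate adjustment in a randomised trial improves precision without disturbing the comparison only if the covariates could not have been influenced by the allocation. Two items on the list clearly fail that test, in different ways.

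- **In-hospital medications.** The allocation is a choice between nitrate and loop diuretic intensity, so these can include the study treatment or lie on its path to the outcome. Holding them fixed removes part of the effect under test. The exposure data will exist: 10.4.2 plans a summary of loop diuretic doses by treatment group.
- **Discharge medications.** These are chosen after the endpoint has been measured, so they cannot mediate it. They can be a consequence of it, and conditioning on a consequence of the outcome also distorts the arm effect.

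For four further items no time point is given: the second mention of renal function (listed apart from baseline renal function), hemoconcentration, physical examination and other vital signs. A later renal value is a real possibility, because 2.3.1 plans to record eGFR before discharge when it is available.

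At stake is the only model in the primary-endpoint text of 10.4.3 that contains the treatment indicator, in a pilot meant to inform a definitive trial.

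**Working it through.** **1. Reproduce the plan's own figure.** Section 10.5 says "This pilot study is powered to show a difference of at least 7 B-lines between treatment arms" and "we will have 82% power to detect an effect size of 0.7 on the number of B-lines", with 35 per arm and two-sided alpha 0.05. A difference of 7 at effect size 0.7 implies SD = 7/0.7 = 10.

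- SE of the unadjusted difference = 10 × √(2/35) = 2.39.
- Noncentrality = 7/2.39 = 2.93. With 68 df the exact t-test power is 82.3% (normal approximation 83.4%). The stated 82% reproduces.

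**2. A covariate on the treatment path (in-hospital medication).** The documents give no relation between drug exposure, arm and B-lines, so these inputs are assumed. Exposure M differs by 1.5 within-arm SDs between arms and carries a share f of the -7 B-line effect. The model is linear.

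- Squared correlation of M with arm = (1.5²/4)/(1.5²/4 + 1) = 0.5625/1.5625 = 0.36.
- Slope of B-lines on M: b = -7f/1.5.
- Residual SD = √(100 - b²).
- Adjusted arm effect = -7(1 - f).
- Adjusted SE = residual SD × √(2/35)/√(1 - 0.36).

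For f = 0.5: b = -2.33, residual SD = 9.72, SE = 9.72 × 0.239/0.8 = 2.91, effect = -3.5, ratio = 1.20, power about 22%.

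Power and selection frequency below come from 4,000 simulated trials per row.

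| Share of effect carried by M | Adjusted effect (B-lines) | Power for arm | M passes univariate screen |
|---|---|---|---|
| 0% | -7.0 | 63% | 39% |
| 25% | -5.2 | 42% | 69% |
| 50% | -3.5 | 22% | 91% |
| 75% | -1.8 | 9% | 99% |
| 100% | 0.0 | 5% | 100% |

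Unadjusted power in the same simulations was 82% to 84%. The screen admits the variable most often where it does most harm.

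**3. A covariate that follows the outcome (discharge medication).** Assume its within-arm correlation with the B-line count is c. The adjusted effect is -7(1 - c²): -6.4, -5.2 and -3.6 for c = 0.3, 0.5 and 0.7. Simulated power is 78%, 68% and 51%.

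**4. Logistic version.** Take the outcome as B-lines at or below 15, with assumed rates of 36% and 64%. The large-sample odds ratio for arm is about 3.1 unadjusted. After adjusting for M it is about 1.8 with half the effect mediated and 1.0 with all of it mediated. The direction matches step 2.

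**5. How many terms fit.** With 70 patients, event rates of 25%, 40% and 50% give 17.5, 28 and 35 events. The cap then allows 1, 2 or 3 terms including treatment, that is 0, 1 or 2 covariates. A post-randomisation variable could therefore be the sole adjustment.

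**6. Baseline adjustment for comparison.** One baseline covariate with within-arm correlation 0.3, 0.5 or 0.7 with the outcome leaves the estimate at about -7.0 and gives power of 85%, 92% or 98%.

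**The case against.** **The section may be prognostic.** The primary endpoint is a count, which a logistic model does not analyse directly. The same text speaks of groups with and without events, ROC curves and predictive values, and discharge medications would be a natural covariate for a 30-day outcome. This has force: a reader might infer that the plan's primary analysis is itself wrongly adjusted, and the documents do not establish that. The model's outcome and its events are undefined. The objection does not clear the text, though. The model stands under the primary efficacy heading, it includes the treatment indicator, and no unadjusted between-arm test of the B-line count is named there.

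**The wording is permissive and the study is a pilot.** True, but the entry rule itself is firm once a variable passes the screen. The plan also claims power, and 10.4.1 states that "two-sided p values < 0.05 will be considered statistically significant, without regard to multiple comparisons".

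**Most listed items may be baseline.** Partly right. Baseline renal function and baseline blood pressure are labelled so, and electrolytes, natriuretic peptide, troponin and eGFR are screening items in the 7.3.4 schedule. Only the two medication items are clearly post-randomisation.

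**Drug dose as near-collinear with arm.** A reader might infer this and deflate the 82% by a variance inflation factor alone. The documents do not support it. Correlations of 0.8 and 0.9 with arm need dose gaps of about 2.7 and 4.1 within-arm SDs (2 × √(r²/(1 - r²))). No such figures are given, and 2.3.1 allows rescue with either drug. Such a calculation also ignores the residual variance that a covariate related to outcome would remove.

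**Selection alone as a source of over-favourable p-values.** This too is tempting and not shown. Choosing up to two of ten baseline covariates by univariate significance, in a linear model with no treatment effect and 35 per arm, gave type I error close to 5%. The fault is the timing of the covariates.

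**Conclusion.** The point holds for the logistic regression in 10.4.3 as written. Its rule allows in-hospital and discharge medications, and possibly four undated items, to be adjusted for alongside treatment. That can bias the arm effect and does not serve the stated aim of precision.

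The direction follows from the design; the size does not. The halved effect and the fall in power to 22% depend on an assumed 1.5 SD exposure gap, 50% mediation, a linear model and the variable being selected. Other assumptions give anything from no bias with some loss of power to complete removal of the effect.

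It does not follow that every between-arm result is compromised. The chi-square or Fisher comparison of B-lines at or below 15, in the secondary-endpoint text, is unadjusted and unaffected, and the sample-size figure of 82% stands.

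**What to change.** In 10.4.3, for any model that estimates the treatment effect:

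1. State that covariates are restricted to variables measured before randomisation.
2. Name a short fixed list, for example baseline B-line count and hospital, and let it replace the univariate screen.
3. Delete in-hospital medications, discharge medications and any post-baseline renal function or hemoconcentration. If physical examination, vital signs or renal function are kept, specify the baseline value.
4. Label any model that uses post-randomisation variables as exploratory prognostic work, and do not report its treatment coefficient as the strategy effect.

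The cost is SAP wording only: no extra patients, visits or data, and the planned N of 70 is unchanged. The fix does not close the separate gap that the logistic outcome is undefined and no between-arm test of the B-line count is named; that needs its own sentence in the plan.

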10.2 STATISTICAL HYPOTHESES

- *Hypothesis 1a: Nitrate intense treated patients will have less congestion, defined by LUS B-lines, than diuretic intense patients at 6 hours after start of treatment.*
- *Hypothesis 1b: Nitrate intense treated patients will have greater dyspnea relief than diuretic intense patients at 6 hours after start of treatment.*
- *Hypothesis 2: Each site (n=3) will enroll ~2 patient per month for 12 months.*

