Dyspnea will be assessed at the baseline and 6 hours later (or closest time point prior to ER discharge using two instruments. Dyspnea will also be assessed at any time between D2 and D/C. A 7-point Likert scale to determine change from baseline: 1) markedly worse, 2) moderately worse, 3) minimally worse, 4) no change, 5) minimally improved, 6) moderately improved, 7) markedly improved. However, patients may not recall accurately how they felt at baseline or be uncertain about when baseline was supposed to be. Also, patients with severe symptoms who don't respond and patients whose symptoms were initially mild and have little room to improve may end up with similar change scores. Accordingly, symptoms were also assessed using an absolute scale. Change in dyspnoea can be calculated by subtracting scores. A 5-point Likert scale was used to document patients' current status: 1) not short of breath at all, 2) mildly short of breath, 3) moderately short of breath, 4) severely short of breath, 5) very severely short of breath.

Patients were placed at 45 degrees for all questioning. If patients were recently up and walking, at least 2 minutes of equilibration is required.

Change scores between responses at baseline and 6 hours on the 5-point Likert scale items and the VAS were calculated by subtracting the baseline value from the 6-hour value. These change scores were categorized as improvement, worsening and no change. Fisher's exact tests were used to compare the 3 groups by either definition on changes in the 5-point Likert scale

2. The comparison of binary endpoints (B-lines ≤ 15) will be performed using Chi-square or Fishers exact test, as appropriate.

As 15 B-lines have been previously shown to be associated with worse outcomes, a difference of 15 B lines will be considered significant for this study.

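### Dyspnea, the basis of Hypothesis 1b, is collapsed to three categories and given an unordered Fisher test, in text that cites an unlisted VAS and leaves the 7-point scale without a test

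*Combined protocol and SAP*

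**What the plan says.** Section 4.2.1 lists two main secondary endpoints: dyspnea on a 5-point and a 7-point Likert scale, and reaching 15 or fewer B-lines. Section 10.2 attaches Hypothesis 1b to dyspnea: "Nitrate intense treated patients will have greater dyspnea relief than diuretic intense patients at 6 hours after start of treatment".

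The analysis is in Section 10.4.3, under the secondary endpoints. It describes two instruments: a 7-point scale of change from baseline and a 5-point scale of current state. It then says that change scores on "the 5-point Likert scale items and the VAS were calculated by subtracting the baseline value from the 6-hour value". Next, "These change scores were categorized as improvement, worsening and no change". Finally, Fisher's "exact tests were used to compare the 3 groups by either definition on changes in the 5-point Likert scale". No test is named for the 7-point scale.

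Section 10.4.1 applies to every test: "two-sided p values < 0.05 will be considered statistically significant, without regard to multiple comparisons". Section 10.4.4 plans a proportional-odds model for days alive and out of hospital (DAOOH) and notes that it allows baseline adjustment to gain power.

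**The concern.** There are two separate problems.

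- **The text cannot be programmed as it stands.** It analyses an instrument that the endpoint list and schedule do not contain. It compares three groups in a two-arm trial under two definitions that are never given. It is silent on one of the two scales that make up the endpoint.
- **The one test that is named suits the hypothesis poorly.** Hypothesis 1b is about the degree of relief. The collapse keeps only the sign of the change, and Fisher's test then treats the three signs as unordered labels. Section 10.4.3 adds the 5-point scale because patients with very different courses can end up with similar change scores, yet the collapse brings that problem back: a move from 5 to 1 and a move from 3 to 2 become the same result.

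At stake is whether the pilot can say anything useful about dyspnea. Section 3 gives the trial's purpose as supplying what a definitive trial needs. A p-value from a collapsed table gives no ordinal effect estimate to plan from.

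**Working it through.** **Inputs from the documents.** Two arms, 1:1 (Section 4.1); 35 per arm (Section 10.5); two-sided 0.05 (Sections 10.4.1 and 10.5). No effect size, response distribution, improvement rate or baseline-to-6-hour correlation is given for dyspnea, so all of these are assumed below.

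**1. The plan's own power figure.** Section 10.5 says "With a total of 70 subjects (i.e. 35 in each arm), we will have 82% power to detect an effect size of 0.7". This refers to B-lines. The noncentrality is 0.7 × √(35/2) = 2.928. The normal approximation gives Φ(2.928 − 1.960) = 83.4%, and the noncentral t gives 82.3%. The stated 82% reproduces. It is the only power figure in the documents.

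**2. The text side by side.**

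| Item | Endpoint list (4.2.1) and schedule (7.3.4) | Dyspnea analysis (10.4.3) |
|---|---|---|
| Instruments | 5-point and 7-point Likert | 5-point Likert and a VAS in the change scores |
| Test, 5-point | – | Fisher's exact on three categories |
| Test, 7-point | – | none named |

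**3. What the test uses.** The exact p-value for a 2×3 table depends only on the cell counts given the margins. Relabelling the three columns leaves it unchanged, so the order worse, unchanged, improved plays no part in it.

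**4. Simulation, 5-point scale.** 35 per arm, 2,000 trials per row. Assumed baseline mix is 10/30/40/20% in categories 2 to 5. The change has an SD of one category, and the effect is in units of that SD. Relative loss = 1 − power(Fisher) / power(Wilcoxon), computed before rounding.

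| Controls improving | Effect | Fisher, 3 categories | Wilcoxon, full change score | Relative loss |
|---|---|---|---|---|
| 31% | 0.5 | 34.4% | 48.1% | 29% |
| 50% | 0.5 | 29.4% | 46.5% | 37% |
| 69% | 0.5 | 22.1% | 43.4% | 49% |
| 84% | 0.5 | 11.5% | 39.7% | 71% |
| 31% | 0.7 | 58.5% | 74.0% | 21% |
| 50% | 0.7 | 52.6% | 74.1% | 29% |
| 69% | 0.7 | 43.0% | 73.1% | 41% |
| 84% | 0.7 | 19.3% | 62.4% | 69% |

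With no effect, neither test was materially above 5%. In the row with 69% improving and an effect of 0.7, a Wilcoxon test on the three categories has 54.3% power. Collapsing therefore costs 73.1 − 54.3 = 18.8 points, and ignoring order a further 54.3 − 43.0 = 11.3 points.

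**5. Simulation, 7-point scale, if the same three-category test were applied.** Under proportional odds with an odds ratio of 3, Fisher against Wilcoxon is 56.3% v 70.2% (30% of controls improving), 49.3% v 70.4% (45%), 40.9% v 70.7% (60%) and 29.1% v 70.8% (75%). The losses are 20%, 30%, 42% and 59%. The smallest loss in steps 4 and 5 is 17% (odds ratio 3.5, 30% improving: 68.9% v 82.6%).

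**6. Against a baseline-adjusted analysis.** 5-point scale, 1,500 trials per row, latent correlation 0.4, effect in latent SD. Losses here are computed from the rounded powers.

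| Controls improving | Effect | Fisher | Wilcoxon on change | Adjusted rank | Loss v adjusted |
|---|---|---|---|---|---|
| 45% | 0.5 | 27% | 43% | 54% | 50% |
| 45% | 0.7 | 45% | 67% | 81% | 44% |
| 65% | 0.5 | 22% | 42% | 54% | 59% |
| 65% | 0.7 | 39% | 67% | 82% | 52% |
| 83% | 0.5 | 10% | 37% | 53% | 81% |
| 83% | 0.7 | 18% | 61% | 81% | 78% |

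**7. Wider grid.** Same baseline mix, correlation 0.36 to 0.75, about 36% to 86% of controls improving, effects 0.5 to 0.7 SD. Fisher was weaker in every setting. The relative loss ran from about 10% to about 80% against Wilcoxon on change, and from about 13% to 84% against the adjusted rank analysis.

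**The case against.** This is a small exploratory pilot, sized on B-lines alone and testing without multiplicity control. Dyspnea was never powered, so low power for it breaks no promise. That stands, and it limits the weight of the point. It does not make the text executable, and it gives no reason to prefer the weaker analysis of data already collected.

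Several stronger readings are tempting, and the documents do not support them:

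- *The plan loses half its power for Hypothesis 1b.* A loss of about half or more arises mainly when most patients in both arms improve or when the baseline-to-6-hour correlation is low. No section gives an improvement rate or a correlation. At the mild end the loss is near 10%.
- *The three groups are a third arm carried over by mistake.* The phrase directly follows the three response categories and may mean those. It is ambiguous, not a proven error in the number of arms.
- *The analysis cannot show direction.* A 2×3 table displays the proportion improved in each arm, so direction is visible. What is true is narrower: the p-value makes no use of category order.
- *Dyspnea is the main secondary endpoint.* It is one of two.

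The choice between proportional odds and rank ANCOVA is partly preference. Either meets the point.

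**Conclusion.** The point holds, and it should be acted on. The drafting faults rest on the text alone and need no assumption: an unlisted VAS, unexplained groups and definitions, and no test for the 7-point scale. The choice of a collapsed, unordered test for a hypothesis about degree of relief is also plain from the text.

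The direction of the power loss is firm, since Fisher was weaker in every setting with an effect. Its size is not fixed by the documents. It should be quoted only as the step 7 range, with those assumptions beside it.

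**What to change.** Rewrite the dyspnea paragraph of Section 10.4.3 in the future tense:

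- Name one scale and one time point to decide Hypothesis 1b, for example the 5-point score at 6 hours.
- Compare the two arms on the uncollapsed score with a proportional-odds or rank-ANCOVA model adjusted for the baseline score. Section 10.4.4 already allows this kind of model for DAOOH.
- Analyse the 7-point score at 6 hours by Wilcoxon or proportional odds, labelled as supportive.
- Delete the VAS and the phrase about three groups and either definition.
- Keep the improved, unchanged and worse table by arm as description.

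The cost is analysis-plan wording, with no new data, visits or patients. There is a small downside: the proportional-odds assumption needs checking, and an odds ratio is less direct to read than a percentage improved. The descriptive table covers the second.

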For years, the lungs have been considered ‘off-limits’ to ultrasound: with aerated lungs, the ultrasound beam is reflected and scattered due to acoustic mismatch.^{57,58} However, in the setting of pulmonary congestion, extra vascular lung water (EVLW) can be directly visualized and quantitated.⁵⁸⁻⁶⁰ Lung ultrasound measurement of B-lines are an objective, semi-quantitative measure of extra vascular lung water (EVLW).⁶⁰ B-lines are well-defined, vertical echogenic lines, originating from water-thickened interlobular septa.⁶⁰ (Figure 1) They are a marker of congestion.

LUS improves diagnostic accuracy and is highly reproducible.⁶¹⁻⁶⁷ Intra and inter-observer variability of B-line capture and summary have been reported as low as 5.1% and 7.4%, respectively.⁶⁸ In a recent meta-analysis, LUS was the best test to affirm the diagnosis of AHF, more than natriuretic peptide (NP) (likelihood ratio positive for the diagnosis of AHF by LUS was 7.4 (95% CI 4.2-12.8) and LR negative 0.16, (95% CI 0.05-0.51)).⁶¹ This may reflect the additional value of LUS when patients have chronically elevated NP levels. Recent guideline and consensus statements also support the use of LUS for diagnosis.⁶⁹⁻⁷³

Importantly, B-lines are a dynamic marker. In dialysis patients, B-lines decrease markedly pre/post dialysis.⁷⁴ In AHF patients, B lines generally decrease throughout hospitalization.^{75,76} However, persistence of B-lines pre-discharge identifies patients at higher risk for worse outcomes.^{76,77} B-lines even outperformed BNP as a prognostic marker.⁷⁵ Finally, serial measurement of B-lines are both easy to learn and perform.^{62,63,78-80} LUS is also low cost, and does not involve radiation. Computerized diagnostic aids have already been pilot tested with excellent results, demonstrating the ease of B-line scoring.⁸¹ Hand held machines perform as well as a standard ECHO platform or US machines.^{63,82} **The ease of LUS will facilitate its generalizability and dissemination.** Non-physicians may be future users of bedside LUS assessment, further supporting its generalizability.

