4 STUDY DESIGN AND ENDPOINTS

4.1 DESCRIPTION OF THE STUDY DESIGN

A two-site, prospective, randomized, pilot trial comparing a nitrate intense vs. diuretic intense strategy. All potential ED patients will receive an initial LUS scan. Performing LUS is within the standard of care and will be done at no cost to patients. It is not frequently used however, either for diagnosis, prognosis, or to guide clinical therapy. However, treating clinicians will be blinded to these results. If clinicians choose to perform their own LUS, those patients will not be excluded. Patients who provide written informed consent and meet all inclusion and no exclusion criteria will be randomized 1:1 to either study arm. For randomized patients, study protocol will continue until there is a decrease in B-

lines to ≤ 15 or 6 hours of care has been delivered. Subjects who are hospitalized prior to the completion of the 6 hour protocol may continue on the protocol until the six hour treatment window is concluded. All images will be stored and overread by an independent, expert ultrasonographer blinded to treatment arm.

Safety of patients are paramount. If a potential life threatening etiology is identified, the clinical team will be made aware immediately, irrespective of randomization arm. These occurrences will be recorded in the eCRF. While this will be a rare event, we will a priori establish that an additional patient will be accrued into the study and an additional modified intent to treat population for analysis will be performed, excluding these patients where a life-threatening etiology was identified (i.e. pericardial tamponade).

For patients who do NOT meet eligibility criteria, the results of their LUS will be provided to the clinical team as requested.

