4.2.1 PRIMARY ENDPOINT

The total number of B-lines at the conclusion of ED AHF management

Main Secondary Endpoints:

Dyspnea will also be assessed using a 5-point and 7-point Likert scale.

B-lines ≤ 15 at the conclusion of ED AHF management

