5 STUDY ENROLLMENT AND WITHDRAWAL

5.1 PARTICIPANT INCLUSION CRITERIA

- 1) Age ≥ 21 years
- 2) Presents with shortness of breath at rest or with minimal exertion
- 3) Clinical diagnosis of AHF and presence of > 15 total bilateral B-lines distributed in at least 4 zones on initial LUS
- 4) Hx of chronic HF and any one of the following:
 - i. Chest radiograph consistent with AHF
 - ii. Jugular venous distension
 - iii. Pulmonary rales on auscultation

- iv. Lower extremity edema
- v. BNP > 500pg/mL

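### The comparison of patients reaching 15 or fewer B-lines takes no account of the entry count, which costs power but does not bias the result

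*Combined protocol and SAP*

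**What the plan says.** Section 5.1 requires "presence of > 15 total bilateral B-lines distributed in at least 4 zones on initial LUS". Section 4.2.1 lists as a main secondary endpoint "B-lines ≤ 15 at the conclusion of ED AHF management". The analysis text in 10.4.3 is one sentence: "The comparison of binary endpoints (B-lines ≤ 15) will be performed using Chi-square or Fishers exact test, as appropriate".

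Earlier in 10.4.3, under the primary endpoint, the plan adds that "Potential covariates will also be considered in a logistic regression setting to improve precision". The list that follows covers co-morbidities, medications, renal function, sodium, natriuretic peptide, troponin and blood pressure, with some further variables as options. The baseline B-line count is not named. Selection is data-driven: "Covariates with univariately significant association with the outcome will be included together with the treatment indicator in a logistic regression model". The number of terms, treatment included, is capped at one per 10 events. The text does not say which binary outcome this model is for. The same section says of B-lines that "Both absolute number and relative change will be evaluated", without naming a model.

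Section 10.6.1 describes block randomisation by site and mentions no stratification by B-line count.

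**The concern.** On the count, every randomised patient starts as a non-responder, but at very different distances from the target. A test that ignores the starting count treats a patient who goes from 16 to 15 as a success and one who goes from 70 to 16 as a failure. It also leaves a plausible predictor of response, measured on every patient before randomisation, out of the comparison. With 35 per arm, a chance difference between arms in entry counts can move the responder difference by several points in either direction, and nothing in the named test corrects for it.

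The plan accepts this principle elsewhere. In 10.4.3 it notes that patients with mild initial dyspnoea have limited scope to improve. In 10.4.4 it values baseline adjustment as a source of power for days alive and out of hospital. Neither idea is carried over to the B-line responder endpoint. At stake is the efficiency and readability of a main secondary result in a pilot meant to inform a definitive trial.

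**Working it through.** **Inputs from the documents.** Entry above 15 lines in at least 4 zones (5.1); response at 15 or fewer (4.2.1); 1:1 allocation (4.1); 35 per arm, two-sided alpha 0.05, effect size 0.7, difference of 7 lines, 82% power (10.5). No baseline distribution or responder rate is given.

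**1. The plan's own figure.** Noncentrality = 0.7 × √(35/2) = 2.93 on 68 degrees of freedom; power = 82.3%, which reproduces the stated 82%. The implied SD is 7/0.7 = 10 lines. This power is for the total count. None is stated for the responder endpoint.

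**2. Fall needed to reach 15** (entry count − 15, and as a share of entry):

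| Entry count | Lines to lose | Share |
|---|---|---|
| 16 | 1 | 6% |
| 20 | 5 | 25% |
| 30 | 15 | 50% |
| 40 | 25 | 63% |
| 80 | 65 | 81% |

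**3. Simulation A (assumed).** Baseline = 16 + gamma, mean 36, SD 12; follow-up = 55% of baseline × lognormal error; treatment effect 0.3 log units; 35 per arm; 1,500 trials. With no effect and error SD 0.5, response by baseline tertile is 60%, 35% and 15%.

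| Error SD | Chi-square | Logistic on arm and log T00 | Gain |
|---|---|---|---|
| 0.5 | 37% | 50% | 13 points |
| 0.3 | 60% | 82% | 22 points |

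Independent re-runs gave 37% against 45–48%, and 59% against 79–81%. Fisher's test gave 29% and 50%.

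**4. Simulation B (different assumptions).** Baseline = 16 + gamma with mean/SD of about 26/10, 36/15 or 56/30; proportional fall with SD 25 points, mean 40% against 55%.

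| Baseline | Fisher | Chi-square | Adjusted logistic | Gain over chi-square |
|---|---|---|---|---|
| 26/10 | 25.6% | 33.7% | 41.5% | 7.8 points |
| 36/15 | 23.5% | 31.8% | 43.3% | 11.5 points |
| 56/30 | 23.9% | 32.1% | 41.1% | 9.0 points |

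**5. Weaker dependence.** When follow-up depends only half as strongly on baseline, the gain falls to 3–7 points; when it does not depend on baseline, to about 2.

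**6. No treatment effect.** Simulation A rejects in 4–5% of trials for both methods. Simulation B gives 4.5–6.2% for chi-square, 2.3–3.2% for Fisher and 5.2–6.4% for the adjusted model, with Monte Carlo error of about 0.6 points.

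**7. Chance imbalance.** In simulation B with no effect, a 1-SD imbalance in mean log baseline moves the responder difference by 4–6 percentage points and explains 20–26% of its chance variation.

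**8. Room for one covariate.** Arm plus T00 makes two terms, so the plan's rule needs 2 × 10 = 20 events, or 20/70 = 29% response. At the 37.5% seen in the middle scenario of simulation B, 0.375 × 70 ≈ 26 events: room for two terms and no more.

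**9. Why the same reader.** Under 17.3 investigators cannot see Core Lab reads until database lock, so entry rests on the site count. The cap per sector is 20 in 17.1 and 10 in 17.3. If site and Core Lab used different caps, one fully white zone plus one line in each of three others would be 20 + 3 = 23 on one scale and 10 + 3 = 13 on the other: eligible on the first and already at target on the second. The two sections must be reconciled.

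**The case against.** Much of the opposing case stands.

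- **Validity.** Allocation is randomised and the error rate is near nominal. A reader might infer that the endpoint produces a false treatment effect; it does not. Chance imbalance is already inside the 5%.
- **Complementary cut-offs are not a defect.** They ensure that nobody meets the target on the entry read. Section 10.4.3 regards 15 as an established threshold, and reaching an absolute state is a legitimate endpoint. The patient who falls from 70 to 16 is captured by the primary total count.
- **Success as mainly a matter of entering near the cut-off.** This is a tempting reading, but no baseline distribution is given. In simulation B, baseline count predicts success with an AUC of 0.78–0.89 and the patient's own proportional fall with 0.82–0.88, so the two matter about equally. Simulation A cannot settle it, because it builds the dependence in.
- **Reader noise.** Section 2.2 says "Intra and inter-observer variability of B-line capture and summary have been reported as low as 5.1% and 7.4%, respectively". These are favourable values from a cited study and are not defined as coefficients of variation. One line in 16 is 6.25%, between the two figures. They do not give this trial's misclassification rate.
- **Time to 15 or fewer.** It may seem to share the problem, but 10.4.4 names no analysis for it.
- **Requiring a minimum fall as well.** Section 10.5 plans on 7 lines, while 10.4.3 calls 15 lines significant. The documents do not support either as a responder rule.

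The logistic model in 10.4.3 is only a partial answer: its outcome is unclear, T00 count is not named, and covariates are picked by significance.

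**Conclusion.** The point holds as one of efficiency. The responder comparison is unadjusted, the T00 count is not provided for elsewhere in its analysis, and the fall needed for success varies from 1 line to many times that. The cost is lost power and exposure to chance imbalance, not bias. The gain from adjustment is about 8 to 22 points over chi-square if follow-up is roughly proportional to baseline, and about 2 to 7 points if the link is weaker or absent. Those figures rest on assumed baseline distributions, response patterns and effect sizes; only the direction is well supported. The endpoint is secondary and the trial an exploratory pilot, so the point does not threaten the main conclusion. It is worth acting on because the change is cheap.

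**What to change.** In 10.4.3, make the main comparison of B-lines at 15 or fewer a logistic regression on arm and log T00 B-line count. Assign T00 count in advance as the one covariate, in place of selection by univariate significance. State whose counts are analysed, and take T00 and follow-up from the same reader on the same per-sector cap. Continue to report raw proportions by arm with Fisher's exact test. If there are fewer than 20 events, use Fisher's test, or a penalised logistic model, as the main comparison, and name in advance which; this follows the plan's own limit of 10 events per covariate.

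**Cost.** SAP wording only, with no added procedure, if the site counts are used. If Core Lab counts are used, first confirm that they exist for every T00 scan: 4.1 says all images are overread, whereas 17.3 says 20% of clips are reviewed. The odds ratio becomes conditional on baseline count and will not match the one from the raw table, which is a further reason to keep showing the proportions.
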